4.6.1.2 Diarrhea

If diarrhea occurs during therapy, patients should initiate loperamide (or equivalent) 2 mg by mouth every 2 hours during the waking hours. The rapid introduction of loperamide (or equivalent) at the first signs of diarrhea is strongly encouraged. Testing for *Clostridioides difficile* (*C. difficile*) should start with first episode of diarrhea. Should testing indicate the presence of *C. difficile*, appropriate antibiotics targeting this infection should be initiated. Should testing exclude the presence of *C. difficile*, loperamide should be continued. Once the diarrhea is controlled, the time interval of loperamide may be titrated to a frequency that adequately controls the diarrhea. The diarrhea observed with alvocidib almost always resolves following completion of therapy, so treatment with loperamide following completion of therapy will not be required in most patients. If loperamide (or equivalent) does not control diarrhea, cholestyramine (or equivalent) 5 gm orally four (4) times daily may be added. For patients developing diarrhea during alvocidib administration, subsequent treatments should include a similar diarrhea prophylaxis. If diarrhea is not controlled with the above prophylactic regimen and is grade 2 or greater, therapy should be held until diarrhea has resolved. **Replacement of excessive fluid losses should be done unless otherwise clinically indicated.**

4.6.1.3 Nausea/Vomiting

Antiemetics (ie, 5-hydroxytryptamine [5-HT₃] receptor inhibitor or other antiemetic medications) are permitted according to standard practices at each investigational site.

4.6.1.4 Infection Prevention

Prophylactic antibiotics including levofloxacin (or equivalent) 500 mg orally once daily and valacyclovir (or equivalent) 500 mg orally BID each day should be administered to patients in all treatment arms at the start of chemotherapy. Alternative prophylactic antibiotic or antiviral therapy is left to the discretion of the treating physician and according to institutional standards. For guidance on possible *C. difficile* infections, refer to *Section 4.6.1.2*.

Antifungal prophylaxis to be administered according to each institution's standard of care.

To prevent cytarabine-related conjunctivitis, corticosteroid eye drops per institutional formulary (eg, prednisolone 0.1%) must begin 1 day prior to institution of cytarabine infusion (ie, Day 6 for ACM; Day 1 for CM) and continue for at least 7 days.

Routine growth factor support is not allowed ≤Day 35 of therapy. Growth factor support can be given at the discretion of the Investigator >Day 35 of therapy in the presence of life-threatening infection with ongoing neutropenia.

Donor lymphocyte infusions are not allowed unless discussed and approved by the medical monitor.

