4.5.3 Treatment Schema

4.5.3.1 Stage 1: Treatment with ACM over Days 1-9

Patients enrolled in Stage 1 will receive treatment with ACM as outlined below:

- **Days 1, 2 and 3: alvocidib (A) - Administer Daily**
30 mg/m² as a 30-minute (± 10 minutes) intravenous (IV) bolus
followed by
60 mg/m² over 4 hours (± 15 minutes) as an IV infusion
- **Days 4 and 5: Rest (no chemotherapy treatment)**
- **Days 6, 7, and 8: cytarabine (C) - Continuous over 72 hours**
2 gm/m² by continuous IV infusion over 72 hours (± 2.5 hours)
(ie, 667 mg/m² daily for total of 2 gm/m²)
- **Day 9: mitoxantrone hydrochloride (M) is administered 12 hours after completion of cytarabine treatment**
40 mg/m² by IV infusion over 1-2 hours (± 10 minutes)

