4.5.3.2 Stage 2: Treatment with ACM or CM

Patients enrolled in Stage 2 will be randomized to either ACM or CM and will receive treatment as outlined below:

Stage 2: Randomized to ACM: Treatment with ACM over Days 1-9

Follow the Stage 1 treatment schema above

Stage 2: Randomized to CM: Treatment with CM over Days 1-4

- **Days 1, 2, and 3: cytarabine (C) - Continuous over 72 hours**
2 gm/m² by continuous IV infusion over 72 hours (± 2.5 hours)
(ie, 667 mg/m² daily for total of 2 gm/m²)
- **Day 4: mitoxantrone hydrochloride (M) is administered 12 hours after completion of cytarabine treatment**
40 mg/m² by IV infusion over 1-2 hours (± 10 minutes)

4.5.3.3 Evaluation After Cycle 1

- Patients who achieve CR, CRi, CRp, or PR after the first cycle (completion of all doses) may receive up to 3 additional optional cycles of treatment.
 - After completing the first cycle of treatment, continued use of mitoxantrone is optional.
 - Mitoxantrone must be omitted from subsequent cycles if the patient's lifetime daunorubicin equivalent exceeds 460 mg/m² (see *Appendix G* for conversion table) or the left ventricular ejection fraction (LVEF) drops below 45%.
- Patients not demonstrating evidence of CR, CRi, CRp, or PR after the first cycle of treatment will be considered for removal from the study, although with permission of the Medical Monitor, induction treatment may continue if clinically indicated and provided there is no evidence of toxicity \geq NCI CTCAE grade 4.
- Perform the End of Study Assessments for those patients who do not continue on study to receive at least one additional cycle of treatment (see *Section 5.5*).

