5.4 Stage 2 Assessments

Sections 5.4.1 – 5.4.5.6 applies for all patients enrolled in Stage 2.

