5.4.1 Assessments Required Prior to First Dose

5.4.1.1 Cycle 1, Day 1 – At Least 10 Hours Prior to First Dose

Perform the following procedures at least 10 hours prior to dosing on Day 1:

- Physical examination including weight (kg) for calculation of body surface area (BSA)
- Assess ECOG PS (*Appendix B*)
- Initiate supportive care measures at least 10 hours prior to first dose in all patients to minimize the likelihood of tumor lysis syndrome:
 - Administer pretreatment IV hydration, oral allopurinol, and oral phosphate binder (see *Section 4.6.1*)
 - Diligent monitoring of urine output **frequently** to ensure that it equals fluid input. If input is greater than output by 10%, administration of diuretics is encouraged. Replacement of excessive fluid losses, including from diarrhea, should be done unless otherwise clinically indicated.
- Record all concomitant medications including all prescription drugs, nonprescription drugs, and nutritional supplements taken since screening.

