5.4.1.2 Cycle 1, Day 1 – Just Prior to First Dose

Perform the following procedures just prior to dosing on Day 1:

- Record vital signs (body temperature, heart rate, systolic and diastolic blood pressures) measured 5-15 minutes prior to the initiation of infusion following a 5-minute rest
- Collect blood for evaluation of laboratory parameters (*Appendix D*):
 - Tumor lysis labs to include electrolytes (sodium, potassium, chloride, and carbon dioxide) as well as creatinine, calcium, lactate dehydrogenase (LDH), uric acid, and phosphorus levels.
 - Coagulation: fibrinogen level
- Collect urine or serum sample for β -hCG pregnancy test for females of child-bearing potential if screening pregnancy test is greater than 72 hours prior to first dose.
- Record all concomitant medications including all nonprescription drugs and nutritional supplements.

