5.4.2 Cycle 1, Day 1 – Dosing

All Patients (regardless of risk of TLS):

- Monitor tumor lysis labs at the start of treatment (alvocidib for ACM, cytarabine for CM) and throughout the treatment cycle according to the schedule outlined in *Section 4.6.1.1*. [Note: there are different blood collection schedules for monitoring of TLS labs for patients at high risk of TLS and for those NOT at high risk for TLS.]
- Monitor fibrinogen levels as clinically indicated.
- Monitor urine output **frequently** to ensure that it equals fluid input. If input is greater than output by 10%, administration of diuretics is encouraged. Replacement of excessive fluid losses, including from diarrhea, should be done unless otherwise clinically indicated.
- Test for presence of *C. difficile* infection at first instance of diarrhea (refer to *Section 4.6.1.2* for additional guidance)
- Administer prophylactic antibiotics and antivirals, corticosteroid eye drops, and antifungals according to *Section 4.6.1.4*.
- Assess for AEs
- Record only those medications (prescription, nonprescription, nutritional supplements) administered in conjunction with an AE.

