5.4.4 Cycle 1 – At Hematologic Recovery

- Assess response by bone marrow biopsy and/or aspiration at time of hematologic recovery (ie, absolute neutrophil count (ANC) >1000 μ L and platelet count >100,000 μ L) or Day 45 (\pm 2), whichever occurs first. If the bone marrow biopsy and/or aspirate is nonproductive or not diagnostic, the procedure must be repeated within 7 days.
 - At time of response assessment, 6 to 8 bone marrow slides will be prepared and sent to the Sponsor. Details regarding the collection and shipping of these slides is provided in the Study Manual.
- Assess for AEs, including tumor lysis clinical symptoms
- Record only those medications (prescription, nonprescription, nutritional supplements) administered in conjunction with an AE.

5.4.5 Cycles 2 - 4

Patients who achieve CR, CRi, CRp, or PR after the first cycle (completion of all doses) may receive up to 3 additional optional cycles of treatment. After completing the first cycle of treatment, continued use of mitoxantrone is optional. Mitoxantrone must be omitted from subsequent cycles if the patient's lifetime daunorubicin equivalent exceeds 460 mg/m² (see *Appendix G* for conversion table) or the LVEF drops below 45%.

Patients not demonstrating evidence of CR, CRi, CRp, or PR after the first cycle of treatment will be considered for removal from the study, although with permission of the Medical Monitor, induction treatment may continue if clinically indicated and provided there is no evidence of toxicity \geq NCI CTCAE grade 4.

However, patients randomized to CM with progressive disease or no response after 1 cycle of CM may cross over to receive ACM. In addition, patients randomized to CM with the best response of a PR after 2 cycles of CM may also cross over to receive ACM. Patients who cross over to ACM may receive up to a combined total (CM + ACM) of 4 cycles.

There is a maximum limit of 90 days between the start of cycles unless otherwise discussed with the medical monitor.

5.4.5.1 Cycles 2 - 4, Day 1 – Within 10 Hours Prior to First Dose

Perform the following assessments in patients receiving subsequent cycles of chemotherapy:

- *If clinically indicated*, administer pretreatment IV hydration, oral allopurinol, and oral phosphate binder (see *Section 4.6.1*)

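### Steroid eye drops must start the day before cytarabine, but the only days printed are cytarabine start days, and the Stage 2 schedule first names the drops on Day 1, one day late for CM

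*Protocol*

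**What the plan says.** **The rule.** Protocol 4.6.1.4 (Infection Prevention) says that, to prevent cytarabine-related conjunctivitis, corticosteroid eye drops "must begin 1 day prior to institution of cytarabine infusion (ie, Day 6 for ACM; Day 1 for CM"), and that they continue for at least 7 days. The Infection Prevention part of the Study Summary gives the same rule and the same two days.

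**When cytarabine starts.** For ACM, section 4.5.3.1 has "Days 6, 7, and 8: cytarabine (C) - Continuous over 72 hours", and section 4.5.3.2 sends Stage 2 ACM patients back to that schema. For CM, section 4.5.3.2 has "Days 1, 2, and 3: cytarabine (C) - Continuous over 72 hours".

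**The Stage 2 lists.** Section 5.4 states that its subsections are one set that "applies for all patients enrolled in Stage 2", so ACM and CM patients are worked from the same lists. Each cycle has two pre-dose steps followed by a Day 1 dosing step. The drops are first named at dosing, in 5.4.2 for Cycle 1: "Administer prophylactic antibiotics and antivirals, corticosteroid eye drops, and antifungals according to *Section 4.6.1.4". Section 5.4.5.3 repeats that line for Cycles 2-4. Each of the two Stage 2 tables in Appendix A has one row for anti-infective prophylaxis and eye drops, with a single mark.

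**The concern.** The rule is mandatory and asks for a one-day lead-in, yet the only days attached to it are the days on which the infusion begins. The bracket is ambiguous:

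- If it explains when cytarabine is given, the sentence is coherent, but the site has to work out the drop start day for itself.
- If it explains when the drops begin, it contradicts the words just before it, and the lead-in disappears in both arms.

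The second problem does not depend on how the bracket is read. In CM, cytarabine is the first drug on Day 1, so the drops are due before any study dose. The shared Stage 2 schedule has no entry at that point. The coordinator reaches the eye-drop line, and its reference to 4.6.1.4, only at Day 1 dosing, after the drops should already have started.

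At stake is one day of prophylaxis against a known cytarabine toxicity. The schedule gap falls on the control arm only.

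**Working it through.** No sample size, power or alpha figure is involved, and the documents print no derived figure to reproduce. The check is day arithmetic plus a count of schedule entries.

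**Inputs**

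- Lead-in: 1 day; minimum course: 7 days (4.6.1.4).
- Cytarabine start: Day 6 for ACM (4.5.3.1), Day 1 for CM (4.5.3.2).
- Infusion length: 72 hours, that is 3 days (same sections).

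**Formulas**

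- Required drop start = cytarabine start day minus 1.
- Infusion end = cytarabine start day + 3. ACM: 6 + 3 = Day 9. CM: 1 + 3 = Day 4.
- Last day of a minimum course = the 7th day, counting the start day as the first (my counting convention).
- Cover after the infusion = last drop day minus infusion end.

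**Required start.** ACM: 6 - 1 = Day 5. CM: the day before Day 1. Neither is printed anywhere in the protocol.

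**Results by reading**

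| Reading | Arm | Drops, minimum course | Lead-in days | Days of cover after infusion |
|---|---|---|---|---|
| Bracket dates the infusion | ACM | Days 5 to 11 | 1 | 11 - 9 = 2 |
| Bracket dates the infusion | CM | Day before Day 1, to Day 6 | 1 | 6 - 4 = 2 |
| Bracket dates the drops | ACM | Days 6 to 12 | 0 | 12 - 9 = 3 |
| Bracket dates the drops | CM | Days 1 to 7 | 0 | 7 - 4 = 3 |
| Stage 2 list followed | CM | Days 1 to 7 | 0 (1 day late) | 7 - 4 = 3 |

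For ACM the Stage 2 list causes no conflict: the Day 1 line comes 5 - 1 = 4 days before the drops are due. The same holds for Stage 1, where every patient receives ACM.

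**Stage 2 entries that name the drops**

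- Pre-dose steps: 0 of 4. Section 5.4.1.1 ("Perform the following procedures at least 10 hours prior to dosing on Day 1") lists hydration, allopurinol and phosphate binder, but not the drops. Sections 5.4.1.2 ("Perform the following procedures just prior to dosing on Day 1"), 5.4.5.1 and 5.4.5.2 do not name them either.
- Entries that do name them: 4, all at Day 1 dosing (5.4.2, 5.4.5.3 and the two Stage 2 tables of Appendix A). The table layout in the text I worked from is partly broken. By cell count the single mark falls in the Dosing column of each table, which agrees with the section text. No footnote gives CM an earlier start.

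**Could an existing pre-dose step carry the instruction?** Not reliably. Section 5.4.5.1 is headed "Within 10 Hours Prior to First Dose", which caps the lead-in at 10 hours. If one day is taken as 24 hours (an assumption), that is 24 - 10 = 14 hours short. The Cycle 1 step in 5.4.1.1 guarantees only 10 hours. The steps just before dosing give less.

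**The case against.** The strongest reply is that the instruction is intelligible as written. The bracket directly follows the mention of the infusion, and the days in it match the infusion days in 4.5.3.1 and 4.5.3.2. On that natural reading nothing conflicts. The Day 1 line in the lists bundles several prophylactic drugs and defers to 4.6.1.4 for timing. The same line stands at Day 1 dosing in Stage 1, where drops are not due until Day 5, so it cannot be meant as a drop start date. What remains is a missing reminder. The damaged table layout also makes Appendix A weaker evidence than the section text.

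Much of this stands. The coherent reading is available, the 1-day rule still governs formally, and 5.4.2 and 5.4.5.3 are the firm support, with the tables only agreeing with them. On a calendar-day reading of the rule, the open-ended step in 5.4.1.1 could also fall on the previous day.

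The reply does not remove the CM problem. A cross-reference reached at Day 1 dosing helps an ACM patient, whose drops are due four days later. It cannot help a CM patient, whose drops were due the day before. The step in 5.4.1.1 could be timed early enough, but it does not mention the drops. Section 4.6 does let sites adjust the dosages of supportive care, but it says nothing about moving start times.

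**Conclusion.** The concern holds, as a minor supportive-care correction worth considering. The protocol never prints the day on which the drops start, and the Stage 2 schedule does not deliver the mandatory lead-in for CM.

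The size is at most one lead-in day per cycle. That day is lost in CM if the Stage 2 list is followed, and in both arms if a site takes the bracket as the drop start day. The infusion is covered in every case, with 2 days to spare after a correct start and 3 after a late one. The cover figures rest on counting the start day as the first of exactly 7 days; a longer course only adds cover. The documents give no ocular event rate, so no clinical effect can be estimated. No endpoint, alpha or analysis is affected.

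**What to change.** 1. In 4.6.1.4 and the Study Summary, replace the bracket with explicit start days: drops start on Day 5 for ACM, including ACM cycles after crossover, and on the day before Day 1 for CM.
2. In the Stage 2 lists (5.4) and both Stage 2 tables of Appendix A, add a separate line for every cycle: CM, start eye drops the day before Day 1. Label it CM, because the lists serve both arms.
3. Do not attach the line to any existing pre-dose step, since none of them ensures a full day of lead-in.
4. Leave the Stage 1 lists and tables as they are.

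The cost is one reworded bracket in two places and one added line in the Stage 2 lists and tables. It needs no new procedure or data and can go in the next amendment.

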4.6.2 Management of Hematologic Toxicities

Adverse events that are moderate to severe in intensity (see *Section 8.1* and *Appendix C* for toxicity grading) and considered possibly or probably related to study drug treatments may result in the termination of study treatment in the affected study patient. Such termination should be reviewed with the Sponsor's Medical Monitor at the earliest possible time (see *Section 8.5*). Following review with the Sponsor's Medical Monitor, the study patient may be permanently withdrawn from the study depending upon the nature and severity of the event.

Adverse events may be treated with concomitant medications, as deemed clinically indicated by the PI. All concomitant medications must be recorded on the appropriate CRF.

4.6.3 Dose Modifications

There will be no dose reductions for alvocidib or cytarabine. The dose of mitoxantrone must be reduced by 50% if the patient's total bilirubin value is >3 mg/dL and <5 mg/dL, and must be omitted if the patient's total bilirubin value is ≥ 5 mg/dL on the day of planned mitoxantrone administration. After completing the first cycle of treatment, continued use of mitoxantrone is optional. Mitoxantrone must be omitted from subsequent cycles if the patient's lifetime daunorubicin equivalent exceeds 460 mg/m² (see *Appendix G* for conversion table) or the left ventricular ejection fraction (LVEF) drops below 45%.

4.7 Concomitant Medications and Therapies

4.7.1 Previous Therapies

During Screening, patients will be asked about all previous therapies and all medications used during the previous 30 days from anticipated first dose. This information will be recorded in the source documentation and appropriate CRF along with the diagnosis or reason for use. If a branded product is being taken, the generic name should be reported, if known.

Subjects will not be enrolled into the study if they have had any previous treatment with alvocidib or other CDK inhibitor, or have received >360 mg/m² equivalents of daunorubicin (see *Appendix G* for conversion table).

4.7.2 Concomitant Therapies

Concomitant therapies are any new or existing medications or therapy taken by the patient including:

- Drugs, including but not limited to, prescription, over-the-counter, birth control pills/patches/hormonal devices, and homeopathic preparations
- Nondrug therapies, including but not limited to, thermal/laser/radiation procedures, vitamins, herbal medicines/supplements.

During the Screening process (up to two weeks prior to anticipated first dose of study drug), information on all concomitant therapies, medications, and procedures will be recorded in the source documents and appropriate CRF along with the diagnosis or reason for use.

Once the patient receives the first dose of study drug, recording of concomitant therapies will be limited to any new medication or modification of an existing medication taken for treatment of an adverse event (AE). These therapies will be recorded in the source documents and appropriate CRF along with the diagnosis or reason for use. Those therapies used for the treatment of an adverse event are to be linked to an AE and documentation of the AE must also be completed (refer to *Section 8*).

If a branded product is being taken, the generic name should be reported, if known.

4.7.2.1 Mandated / Permitted Therapies

Concomitant medications necessary for the health and well-being of the patient and that do not interfere with study assessments are permitted during the study at the Investigator's discretion. This includes the use of appropriate medications for the treatment of AEs and/or concurrent illnesses under the direction of the Principal Investigator. All such therapies must be recorded in the source and on the appropriate CRF.

In patients with rapidly proliferating disease, hydroxyurea may be administered up to the evening before starting treatment in either Stage, but not within 12 hours prior to dosing.

Patients may be allowed on study if they have undergone a diagnostic lumbar puncture (LP) for suspected CNS leukemic involvement. If, at the time of the LP, they received a single dose of intrathecal (IT) chemotherapy, that patient would still be considered eligible for this study so long as the LP was negative for CNS disease. Should the LP indicate positive cytology necessitating continued IT therapy, the patient would be ineligible for study inclusion.

Medications and procedures that are mandatory or permitted during the study are listed in *Section 4.6.1*.

4.7.2.2 Prohibited Therapies

The following medications are excluded from concomitant use:

- Antileukemic therapy (chemotherapy, radiation therapy, immunotherapy) within the last 3 weeks prior to the first study drug administration and during the cycle of study treatment (see *Section 4.7.2.1* for permitting prior hydroxyurea and IT chemotherapy)
- Live vaccines within 14 days prior to first study drug administration, during the study, and for approximately 3 months after the last dose of study drug.
- Donor lymphocyte infusions are not allowed unless discussed and approved by the medical monitor.

4.7.3 Birth Control Requirements for Fertile Patients

Sexually active patients and their partners must use an effective method of contraception associated with a low failure rate during and for at least 6 months after completion of study therapy. The following are considered effective contraceptives: (1) oral contraceptive pill; (2) condom plus spermicide; (3) diaphragm plus spermicide; (4) true abstinence when this is in line with the preferred and usual lifestyle of the subject (periodic abstinence [eg, calendar, ovulation, symptothermal, post-ovulation methods, etc], declaration of abstinence for the duration of exposure to study drugs, and withdrawal are not acceptable methods of contraception); (5) patient or partner surgically sterile; (6) patient or partner more than 2 years post-menopausal; or (7) injectable or implantable agent/device. Male patients enrolled in the study must use a condom to avoid exposing partners to semen, which may contain toxic drugs.

